Lung Cancer Surgery: Decisions Against Life Saving Care - The Intervention

NCT01687738

Protocol Date: May 13, 2011

Most Recent IRB Approval Date: March 29, 2016

Lung Cancer Surgery: Decisions Against Life Saving Care - The Intervention

STATISTICAL ANALYSES

Outcome Measures

Primary Outcome. Whether or not patients undergo lung resection surgery represents the main study outcome. We will conform to the 4 month standard used in the SEER database. To ascertain the result, we will first call patients' physicians to determine whether surgery occurred within the designated time frame. Given the possibility that individual patients could seek other opinions and receive surgical care elsewhere, when appropriate, we will ask the patient, or a family member (if the patient is dead or unavailable), whether surgery was performed by someone other than the index physician. If surgery has not occurred, we will ask for reasons. Through appropriate consent, we will retain the option of confirmatory medical records review. For secondary analyses, we will record surgeries that occur beyond the 4 month threshold.

Secondary Outcomes.

1. One year, post-enrollment survival in surgical and non-surgical groups
2. Satisfaction of patients that received interventions compared to those who did not
3. Patients' perceptions of communication for those patients that received intervention compared to those who did not
4. SF-12 scores at baseline, 6 months post-enrollment and 12 months post enrollment

6. Data Analysis:

Our current plan includes:

Descriptive statistics (means, standard deviations, frequencies, proportions, correlations, and graphical displays) will be computed for all study variables at baseline and post-baseline. The distribution of all outcome variables will be assessed to determine if distributional assumptions are valid. Descriptive statistics will be obtained for all the variables overall and by race and site. Statistical methods for addressing each of the specific aims of the study are detailed in this section. Since several statistical tests are planned, there is the possibility of incurring spurious results if we do not correct for multiple comparisons. All tests are based on a 2-sided alpha of 0.05.

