The main outcome of interest is whether patients undergo surgery is a dichotomous variable, either yes or no. We will compute proportions to estimate the probability of surgery for blacks and whites and compute 95% confidence intervals for the proportions. Since the main outcome is dichotomous, logistic regression for clustered data (clustered within sites) using multiple predictors will be used to assess the simultaneous effect of predictors on the outcome.

Specific Aim 1. To maximize surgical rates for all patients with stage I and II, non-small cell lung cancer who do not have absolute contraindications for lung resection surgery.

hypothesis 1a. a cancer communicator who utilizes active listening and teach-back methods during discussions about lung cancer surgery with newly diagnosed, early stage patients will increase the rate of surgery in Caucasian and African-American patients who do not suffer absolute contra-indications for lung cancer surgery compared to usual care

The primary outcome variable, surgery yes or no, will be compared in the control group randomized to usual care, to the intervention group randomized to the cancer communicator. Bivariate analyses will be performed using the surgical outcome as the dependent variable. Independent variables in these analyses will include important group, demographic variables

such as age, race, marital status, household income, health insurance, gender, and education as well as measures of trust, patient satisfaction, functional status, self-reported health, comorbid illness, perceptions of communication, and the communication intervention. We will use bivariate analyses, including correlations and chi-square tests of association, to make preliminary assessments of the relationships between study variables, overall and by race.

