
hypothesis 1b. the communication intervention will be more effective in patients who score lower in measures of health literacy

Using the logistic regression analyses for clustered data as noted above, the interaction effects of health literacy, S-TOFHLA scores, and intervention group will be tested in all models. . S-TOFHLA scores will be tested as a continuous variable and also, separately, as a dichotomous variable comparing those categorized as inadequate or marginal literacy with those categorized as adequate literacy [103]. Cumulative pre-intervention surgical rates will be compared at all sites with post-intervention rates using Pearson's chi-square test. Post-intervention rates will be compared using test of proportions and changes in proportions from baseline will be compared between surgical and nonsurgical groups using appropriate methods. To determine if the post-intervention rate approaches maximal surgical rates, we will identify patients with high risk co-morbidities, above the age of 80, and need for pneumonectomy or multiple lobectomy in the "no surgery group", subtract this sum from the denominator then re-calculate the surgical rate. We will analyze the secondary specific aim, To measure the effect of the intervention on patients' perceptions of communication and satisfaction with care, by dichotomizing these variables and replacing surgery as the dependent variable in chi-square and logistic regression models as described under the specific aim above.

Specific Aim 2. To reduce the documented difference in lung resection surgery and mortality between African-American and White patients with early stage, non-small cell

lung cancer.

hypothesis 2a. giving physicians who make lung cancer surgery decisions data relating co-morbidity to surgical outcomes will reduce racial differences in surgery

hypothesis 2b. using a real time lung cancer registry to provide physicians race-specific feedback about their surgical treatment of early stage lung cancer patients will reduce racial differences in surgery

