We will analyze patient level cross-sectional dichotomous outcome data using logistic regression growth models. We will both limit analyses to the cancer communicator control group and do an all enrollee analysis by adding a communicator intervention / no communicator intervention predictor variable to the models. First, we will fit a saturated growth model to estimate annual proportions of these outcomes, before and after the registry/feedback intervention, to assess the effects of the intervention on these outcomes by contrasting the proportions before and after the interventions. We will test the null hypothesis that the proportions before and after the intervention are the same. We will repeat this analysis by including "race" and "race x time" interaction in this model to examine changes in these outcomes between the two races and also if there are any differential changes over time. We will test the null hypothesis that the proportions before and after the intervention are the same for each race

Data interpretation: If our data feedback / registry intervention is found to produce an effect in less than the 4 Cancer Centers, it will prompt further examination of the factors that moderate or mediate the relationship between the intervention and completion of cancer treatment. Thus, by conducting an embedded randomized cohort-control study of the Cancer Communicator intervention component, we may be better able to provide more information about the dimensions along which these interventions can or cannot be generalized.

hypothesis 2c. a cancer communicator who utilizes active listening and teach-back methods during discussions about lung cancer surgery with newly diagnosed, early stage patients will increase the rate of surgery in African-American patients more than Caucasian patients compared to usual care.

We will compare post intervention, unadjusted, surgical rates between African-American and White lung cancer patients using chi-square analysis as discussed under Aim 1. We will also perform the maximum rate analysis stratified by race. The regression models described above under Aim 1. We will also apply these analyses to patients in the communicator group alone selecting patients on an intention to treat basis.

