The SF-12 physical and mental component scores will be converted to 0 – 100 scales and utilized as the dependent variable. Baseline scores will be compared first to 6 month scores then 12 month scores using paired t-tests. Generalized linear mixed models for repeated measures data will be constructed in a similar manner as the logistic regression models described above; however, surgical status, race, and comorbid conditions will be forced predictors in these model.

Note that interim analyses regarding specific aims 1 and 2 will be performed at the end of study year 2 then annually. If statistically significant benefits in care are documented on surgical rates and reduction in disparities, the study will be terminated and workshops and individual training sessions of the communication methodologies will be initiated for the care teams at all the study sites.

7. Sample Size

Power computations are computed for post-intervention comparison of proportions. The project anticipates enrolling 496 patients into the study due to constraints on budget, patient availability, and study duration. Thus, we compute the minimal effect size we can detect with statistical power of 80% for our primary aim, AIM 1, using the specified sample size. In computing the effect size, we specify our main outcome as the probability of undergoing surgery for all patients post-baseline as compared to the probability for all patients in the previous study because all groups will receive the data registry and feedback interventions.

Let p_1 be the proportion all patients who undergo surgery in the present study and $p_0 = 0.63$ be the proportion of patients who underwent surgery in the previous study. Using a one-sample test of proportion with 496 subjects overall and significance level of 0.05, we have 80% power to detect a minimally important difference (increase) in surgical rate of $p_0 = 0.63$ to $p_1 = 0.69$. With a sample size of 159 for blacks, we have 80% power to detect an overall increase from $p_0 = 0.55$ (as measured in the previous study) to $p_1 = 0.66$ with significance level of 0.05. With a sample size of 337 for whites, we have 80% power to detect an overall increase from $p_0 = 0.66$ (as measured in the previous study) to $p_1 = 0.73$ with significance level of 0.05.

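### The SAP stops the trial for benefit on repeated, unadjusted 5% tests that it does not name: the 5% level is not guaranteed, although inflation is small if the randomised comparisons are meant

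*SAP*

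**What the plan says.** The interim plan is a note after Specific Aim 4 in SAP section 6 (Data Analysis): "interim analyses regarding specific aims 1 and 2 will be performed at the end of study year 2 then annually". The consequence follows: "If statistically significant benefits in care are documented on surgical rates and reduction in disparities, the study will be terminated". The same sentence adds that care teams at all sites would then be trained in the communication methods. The only significance level is at the start of section 6: "All tests are based on a 2-sided alpha of 0.05". Just before it, the SAP warns that "there is the possibility of incurring spurious results if we do not correct for multiple comparisons", but no correction follows. Neither document gives a stopping boundary, a spending function, an adjusted final level or the last interim look.

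The stopping tests are not identified. For surgical rates the SAP offers three candidates:
- hypothesis 1a, in which the surgical outcome "will be compared in the control group randomized to usual care, to the intervention group randomized to the cancer communicator";
- a chi-square test placed under hypothesis 1b: "Cumulative pre-intervention surgical rates will be compared at all sites with post-intervention rates";
- the one-sample test against 0.63 in section 7 (Sample Size), which that section attaches to Aim 1.

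For disparities there are two: the race-by-time model under hypotheses 2a and 2b, meant to "examine changes in these outcomes between the two races and also if there are any differential changes over time", and hypothesis 2c, that the communicator "will increase the rate of surgery in African-American patients more than Caucasian patients compared to usual care".

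**The concern.** Each extra look at the full 0.05 level gives another chance of a false positive unless the level is shared across looks. Here a positive look ends the trial, so controlled recruitment cannot be resumed. Because the tests are unnamed, two analysts following the SAP could reach opposite decisions on the same data, and the size of the error depends on which tests they choose. A trial that stops early on a nominally significant result also tends to report too large an effect, and the first look would rest on only about 110 patients with known outcomes.

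**Working it through.** **1. The plan's own figure.** Section 7 gives 80% power. For a one-sample test, power = Φ[(|p1 − p0|√n − 1.96√(p0q0)) / √(p1q1)]. With n = 496, p0 = 0.63 and p1 = 0.69 this is Φ[(1.336 − 0.946) / 0.462] = Φ(0.843) = 0.800. For 159 black patients (0.55 to 0.66) it is 0.808, and for 337 white patients (0.66 to 0.73) it is 0.789. The figures reproduce, and they assume one test at the full two-sided 0.05.

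**2. Information at each look (assumed).** Recruitment starts at month 13 (Protocol E) and runs 3 years to 496 patients (Protocol E.2). The outcome takes 4 months. With even accrual, and the window counted from enrolment:
- month 24: (12 − 4)/36 = 22%, about 110 patients
- month 36: (24 − 4)/36 = 56%, about 275
- month 48: (36 − 4)/36 = 89%, about 440
- final: 100%, 496

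The last interim look is unstated, so a schedule without month 48 and one in equal thirds were also run.

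**3. The rule as written.** Stop at an interim look only if both statistics exceed 1.96 in the benefit direction; otherwise test Aim 1 two-sided at 0.05 at the end. The calculation used Brownian-motion simulation with 1,000,000 paths per schedule and correlation. Drift is the expected final z of the disparity test. Aim 1 is null throughout.

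| Correlation | Drift | Four looks | Months 24, 36, final | Equal thirds |
|---|---|---|---|---|
| 0 | 0 | 5.1% | 5.1% | 5.1% |
| 0 | 1.2 | 5.5% | 5.4% | 5.4% |
| 0 | 2.8 | 6.7% | 6.3% | 6.4% |
| 0 | 4 | 7.6% | 7.1% | 7.2% |
| 0.5 | 0 | 5.7% | 5.6% | 5.5% |
| 0.5 | 1.2 | 6.8-6.9% | 6.5% | 6.5% |
| 0.5 | 2.8 | 8.1% | 7.6% | 7.5% |
| 0.5 | 4 | 8.5% | 8.0% | 7.8% |
| Disparity criterion always met | | 8.7% | 8.2% | 7.9% |

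Repeat runs agree to about 0.1 point. With four equally spaced looks the last row is 8.8%.

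**4. How large a drift is plausible for 2c.** Drift = [(black gain) − (white gain)] / √Σ p(1 − p)/n, with 1:1 allocation assumed (79.5 black and 168.5 white patients per arm). An 11-point gain in black patients alone gives 0.11/0.0927 = 1.19. That case has a pooled effect of 159 × 0.11/496 = 3.5 points, so the Aim 1 null is false there. Keeping the pooled effect at zero needs a reversal in white patients: black +7.5 and white −3.5 points give 0.11/0.0937 = 1.17. Drift 2.8 needs +17.4 and −8.2 points, and drift 4 needs +24.3 and −11.5. These are race-by-arm differences of about 26 and 36 points.

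**5. Patient-level simulation with 1a and 2c.** 400,000 trials; the correlation between the two statistics was 0.03-0.06. With no effect, Aim 1 error is 4.9%, against 4.8% for the final test alone. With black +7.5 and white −3.5 points it is 5.5% (four looks) or 5.25% (three).

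**6. Exaggeration on early stopping.** Take gains of 11 points in black and 7 in white patients as an illustration. The true pooled difference is (159 × 0.11 + 337 × 0.07)/496 = 8.3 points. Both 1a and 2c are significant at some interim look in 4.8% (four looks) or 2.7% (three looks) of trials, and at the first look in 1.0%. The mean observed difference at stopping is 15.0 or 17.5 points, which is 1.8 or 2.1 times the truth.

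**The case against.** The strongest reply is that the rule largely protects itself. It needs two criteria at the same look and stops only for benefit. Its stated consequence is to roll out the communication methods, which are the randomised component; the registry, feedback and checklist already reach all sites. That points to 1a and 2c, where inflation is at most about half a point. Even the 5.5% case requires the communicator to lower surgery rates in white patients. Early stops are also rare in the illustrated scenario.

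All of this stands as to size. It does not remove the gap: the rollout clause supports an inference but does not name a test, and section 7 attaches Aim 1 to an uncontrolled one-sample comparison.

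Two stronger readings should be resisted. A reader might infer the familiar inflation from repeated testing, here 10.7-12.4%. That applies only if one criterion were tested and reported alone in either direction at each look, which is not the rule written. A reader might also take 8-9% as the general size. Correlation 0.5 alone gives 5.5-5.7%, even correlation 0.95 with no disparity effect gives only about 7.5%, and drift of 2.8-4 without correlation gives 6.3-7.6%. The upper end needs both together, or a disparity criterion that is nearly always met. The documents establish neither.

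**Conclusion.** The omission is certain and worth correcting; its numerical effect is conditional and probably modest. The 5% level is not guaranteed under the rule as written. If 1a and 2c drive stopping, Aim 1 error is about 4.9% with no effect and at most about 5.5% in the scenarios simulated. For an unspecified pair of tests it is 5.1-5.7% when neither effect is real (correlation 0 to 0.5) and 5.4-6.9% with a modest disparity effect, rising to about 8-8.8% only in the extreme conditions described above. An early stop would happen in about 3-5% of trials in the illustrated scenario and would then overstate the effect about twofold.

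These figures rest on assumed look times, even accrual, 1:1 allocation, the chosen correlations and independent increments from prospective accrual. They may not carry over to the before/after tests, in which the historical data are fixed before the first look.

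**What to change.** Name the test that drives stopping for surgical rates, preferably the randomised 1a comparison because it has a concurrent control, and name the test for disparities. State the last interim look and the final analysis. Apply an alpha-spending boundary at overall two-sided 0.05 to the Aim 1 stopping test, and state the spending convention.

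For example, Lan-DeMets O'Brien-Fleming-type spending uses α(t) = 2[1 − Φ(z/√t)]. Nominal p at 22%, 56%, 89% and 100% information:
- two-sided 0.05 spent as one quantity (z = 1.96): about 0.00003, 0.0085, 0.035 and 0.037 (critical values 4.16, 2.63, 2.11, 2.09)
- 0.025 spent in each tail: about 0.000004, 0.0053, 0.033 and 0.04

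Without a month-48 look, the first convention gives about 0.00003, 0.0086 and 0.047. If a before/after test is chosen, it needs its own information fractions.

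The cost is SAP wording and about 0.5-1.5 points of power: under the first convention, 80% falls to about 78.5% with four looks or 79.5% with three. Aim 1 error then stays at or below 5% whatever the disparity test does, because a second criterion can only remove interim stops. Putting the four-look boundary on both tests, with both still required, is conservative (Aim 1 error about 3.7-4.4%) and is not needed to protect Aim 1. Such a boundary makes a first-look stop very unlikely, which is reasonable with about 110 patients.

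### The interim stopping rule does not name the contrast that triggers it, so a gain shared by both arms could end the trial and roll out the communicator methods

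*SAP*

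**What the plan says.** The note at the end of SAP section 6 says that "interim analyses regarding specific aims 1 and 2 will be performed at the end of study year 2 then annually". The rule follows: "If statistically significant benefits in care are documented on surgical rates and reduction in disparities, the study will be terminated". The consequence it attaches to a positive result, at every site, is that "workshops and individual training sessions of the communication methodologies will be initiated". It names no test, comparator or hypothesis. The only significance level in the SAP's analysis section is general: "All tests are based on a 2-sided alpha of 0.05".

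Aims 1 and 2 contain two kinds of contrast.

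- **Randomised.** Under hypothesis 1a, surgery "will be compared in the control group randomized to usual care, to the intervention group randomized to the cancer communicator". Hypothesis 2c asks whether the communicator helps African-American patients more than Caucasian patients.
- **Before/after.** The text under hypothesis 1b adds a chi-square test of pooled pre- against post-intervention rates at all sites. For hypotheses 2a and 2b, growth models are used "to assess the effects of the intervention on these outcomes by contrasting the proportions before and after the interventions", overall and by race, with a race-by-time term.

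SAP section 7 powers Aim 1 on the second kind. Its main outcome is the surgical rate in all patients against the rate in the previous study, "because all groups will receive the data registry and feedback interventions". Protocol section E gives the comorbidity checklist to all providers at all sites, so this too reaches both arms.

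**The concern.** The action that follows a positive interim result concerns the communicator: randomisation ends and the care teams are trained in its methods. The evidence that can produce a positive result need not concern the communicator at all. If the registry, feedback and checklist raise surgery equally in both arms and the racial gap narrows, the before/after tests of Aims 1 and 2 can both be significant while the arms do not differ. The one randomised question would then be closed early, and its intervention adopted, on data that say nothing about it.

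This is separate from the missing boundary for repeated looks. Spending alpha properly on a before/after contrast would leave the problem in place.

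**Working it through.** **1. The plan's own figure.** One-sample test, power = Φ[(p1 − p0 − 1.96√(p0q0/n)) / √(p1q1/n)]. For 0.63 to 0.69 with n = 496: (0.06 − 0.0425)/0.0208 = 0.84, so 80%. The subgroup figures give 81% (159 Black patients, 0.55 to 0.66) and 79% (337 White patients, 0.66 to 0.73). Section 7 therefore reproduces at two-sided 0.05, as a contrast that ignores arm.

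**2. Timing of looks.** Recruitment starts at month 13 at 165 a year (Protocol sections E and 2). Looks at the end of years 2, 3 and 4 fall at about 165, 330 and 496 enrolled. The last is full enrolment. With the 4-month outcome window, only about 110, 275 and 440 patients are evaluable (165 × 8/12 = 110, and so on).

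**3. Can a shared gain meet both conditions?** Simulation with zero communicator effect, 30% Black patients and z > 1.96 for each test.

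- Surgical rates: z = (p̂ − 0.63)/√(0.63 × 0.37/n).
- Disparity, read as a change in the gap from 0.66 − 0.55 = 0.11: z = [0.11 − (ŵ − b̂)] / √(b̂(1 − b̂)/n_B + ŵ(1 − ŵ)/n_W), where b̂ and ŵ are the observed Black and White rates.
- The two-sample version replaces the fixed rates with chart data at 0.55 and 0.66. It assumes 654 charts, 132 of them Black: two years of the case table in Protocol section C, 2 × 327 and 2 × 66.

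Cumulative probability that both conditions have been met:

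| Rates in both arms | Reference | 165 | 330 | 496 |
|---|---|---|---|---|
| Black 0.66, White 0.73 | fixed | 5% | 13% | 19% |
| Black 0.66, White 0.73 | charts | 3% | 7% | 10% |
| Both 0.69 | fixed | 11% | 34% | 59% |
| Both 0.69 | charts | 6% | 15% | 22% |

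A hand check at 496 shows which condition binds. With 0.66 and 0.73 the overall rate is 0.3 × 0.66 + 0.7 × 0.73 = 0.709, and the pooled test has power Φ[(0.079 − 0.0425)/0.0204] = 96%. The gap falls by only 0.04, with standard error √(0.66 × 0.34/149 + 0.73 × 0.27/347) = 0.046, so the gap test has power Φ(0.88 − 1.96) = 14%.

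Counting only evaluable patients (110, 275, 440) lowers the first row to about 3%, 11% and 18%.

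**4. A looser reading of the disparity condition.** The SAP also tests before against after within each race. If a significant rise in Black patients counts as the reduction, the 0.66/0.73 figures against fixed rates become about 26%, 57% and 81%.

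**5. A randomised trigger for comparison.** With no arm difference, a two-sided 0.05 test favours the communicator in about 2.5% of trials at a single look.

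**6. What early stopping costs.** Power for 0.63 v 0.73, 1:1 allocation assumed: Φ[(0.10 − 1.96√(2 × 0.68 × 0.32/n)) / √((0.63 × 0.37 + 0.73 × 0.27)/n)].

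- n = 82 per arm (first look): (0.10 − 0.143)/0.072 = −0.59, so 28%.
- n = 248 per arm (full enrolment): (0.10 − 0.082)/0.042 = 0.43, so 67%.

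**The case against.** The strongest reply is that the sponsor meant the randomised comparison. Hypothesis 1a leads Aim 1, 2c belongs to Aim 2, and training in communication methods is a sensible consequence only of a communicator benefit. The plan also separates the two effects elsewhere: Protocol section E compares control patients with historical controls to gauge the passive effect of registry and checklist, and the Aim 2 models are run in communicator controls alone and again in all enrollees with a communicator term. An interim analysis of Aim 1 would also produce the arm comparison.

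Most of this stands. A reader might infer that the rule makes the before/after gain the trigger, or that roll-out would go ahead with no randomised evidence in view. The documents do not support either inference: the before/after trigger is permitted, not prescribed. What remains is that nothing ties the stopping rule to 1a or 2c, and section 7 points to the pooled historical contrast.

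A second reply is that the rule needs both conditions. That also stands, and it limits the size. An equal 6-point rise in each race leaves the 11-point gap unchanged and should not count as a reduction in disparities.

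Third, the chart baseline is uncertain. Protocol section D expects 100 to 150 charts per site (400 to 600 in all), and the section C surgery rates average about 71% (weighted by cases), though the protocol calls them overestimates. Against a baseline near 71%, an overall rate of 0.709 would be no rise at all.

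**Conclusion.** The concern holds as an unspecified trigger with a serious possible consequence. As written, a gain common to both arms, with a narrower racial gap, could end the only randomised comparison and start roll-out of the communicator methods without an arm difference.

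The chance depends on how disparity reduction is tested and on the baseline. With a gap-change test and the section 7 target rates it is modest, 13% by the second look against fixed rates and 7% against charts. It becomes large only if the gap closes completely. A reader might take 26%, 57% and 81% as the size of the problem; those figures need a rise in Black patients alone to count as reduced disparity, and the rule does not say that.

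Loss of randomised information concerns the first two looks, since the third is at full enrolment. Adoption without a demonstrated arm difference could follow any look. The figures assume zero communicator effect, 30% Black patients, 1:1 allocation, looks by enrolment count and no interim boundary.

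**What to change.** Add one sentence to the interim note in SAP section 6: termination, and roll-out of the communication methods, can be triggered only by the randomised-arm comparison of surgery (hypothesis 1a, with the race-by-arm interaction of 2c for disparities); before/after results for Aims 1 and 2 are reported at the interim looks but cannot end the randomised trial.

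If this is what the sponsor intended, the change is a clarification. The cost is that early stopping becomes less likely. Even at 248 per arm, the arm comparison has 29% power for the 0.63 to 0.69 difference on which section 7 is built, and an interaction test will have less power than the main comparison.
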